9.3. Vital Signs

Vital signs will be collected at Screening, Days 1, 2, 3, 4, 5, 6, 11, 18, and 25.

Descriptive summaries of observed and change from baseline values will be calculated for systolic blood pressure, diastolic blood pressure, pulse, respiratory rate, and oxygen saturation (SpO₂) by study visit and treatment group within treatment period for patients in Safety Set.

Frequencies and percentages of vital sign interpretation results (normal, abnormal clinically significant, and abnormal not clinically significant) will be summarized by part, treatment group and overall Dasiglucagon group and study visit.

Shifts from baseline for vital sign interpretation results normal, abnormal not clinically significant and abnormal clinically significant will be provided by treatment group within treatment period and study visit.

9.4. Electrocardiograms

An ECG will be performed at Screening and Days 1, 2, 3, 4, 5; 6; 11, 18, and 25. Descriptive summaries of observed and change from baseline values will be presented for continuous ECG measures of heart rate, PQ interval, QRS duration, QT interval, and QTcF interval by study visit and treatment group within part and overall for Dasiglucagon group.

Frequencies and percentage of patients of investigator interpretation of ECG results (normal,

abnormal clinically significant, and abnormal not clinically significant) will be summarized for patients in Safety Set by part, for each treatment group, overall for Dasiglucagon group and by study visit.

Additionally, frequencies and percentage of patients with observed QTcF >450, >480, and >500 msec, as well as change from baseline in QTcF >30, >50, and >60 msec, will be summarized for patients in the Safety Set by part, for each treatment group, overall for Dasiglucagon group and by study visit.

9.5. Echocardiography

An echocardiogram will be performed at Screening and Follow-up.

Frequencies and percentage of echocardiography interpretation results (normal, abnormal clinically significant, and abnormal not clinically significant) will be summarized for patients in Safety Set by study visit.

9.6. Physical Examination

A complete physical examination of body systems according to standard of care and a neurological examination (including cranial nerves, muscle strength and tone, reflexes, coordination, sensory function, and gait, all as applicable for the patient's age) will be performed at Screening, Days 1, 2, 3, 4, 5, 6, 11, 18, 25 and Follow-up.

Frequencies and percentages of physical examination interpretation results (normal, abnormal clinically significant, and abnormal not clinically significant) will be summarized by part, treatment, overall Dasiglucagon group and by study visit for each body system on patients in the Safety Set.

In addition, physical examination results will be summarized in listing.

9.7. Local Tolerability

Local tolerability data will be collected separately from AEs at Days 1, 2, 3, 4, 5, 6, 11, 18, and 25. Data will be collected on the nature of any reaction (including spontaneous pain, pain on palpitation, itching, redness, edema, induration/infiltration, and other type of reaction; other type of reaction will be coded using MedDRA, same version as for AEs), if reaction at injection site, the severity (i.e., mild, moderate, or severe), and any action taken (i.e., no action, interruption of infusion, and other). The likely cause of the reaction will also be collected (i.e., insertion site, drug, adhesive dressing, or other).

The frequencies and percentages of patients with local tolerability findings (nature of reaction, if reaction at injection site, severity, and action taken), collected separately from AEs, will be summarized by part and study visit. Description will be performed only on the Dasiglucagon group.

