
	
Key Secondary Endpoints
 
Part 1, Day 1 to 4
 
The key secondary endpoint of total amount of gastric carbohydrates administered will be analyzed by using a mixed-model regression approach, with treatment and period as fixed effects and patient as a random effect.
 
Safety Analyses
 
Adverse events will be coded using the latest version of the Medical Dictionary for Regulatory Activities (MedDRA). Adverse events that begin after the first dose of trial drug will be defined as treatment emergent. The overall incidence of AEs will be displayed by system organ class, preferred term, and treatment. The incidence of AEs will also be presented by severity and by relationship to the trial drug. Vital signs, clinical laboratory measures (including hematology, biochemistry, and incidence of anti-drug antibodies [ADAs]), 12-lead electrocardiograms (ECGs), echocardiography, physical examinations, and local tolerability data will be summarized by treatment, where applicable. Out-of-range safety endpoints may be categorized as low or high, where applicable.
 
Safety results will be summarized by treatment received within treatment period and part and by trial visit, if applicable.
 
A formal statistical analysis plan (SAP) will be prepared to provide further details on the methods for statistical analysis.
 
No interim analysis is planned.

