13.4.4. Safety and Tolerability Analyses

Safety analyses will be conducted using data from the Safety Population (as defined in Section 13.3). Safety assessments will include the evaluation of AEs; clinical laboratory assessments (hematology, biochemistry, and ADAs); vital signs, physical examinations; ECGs, echocardiography, and local tolerability issues. No formal inferential analyses will be conducted for safety variables, unless otherwise noted.

Baseline is defined as the last nonmissing assessment before the first exposure to trial drug in the trial.

All safety analyses will be summarized by treatment received within treatment period and part and by trial visit, if applicable.

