8.4. Other Efficacy Analysis

8.4.1. CHI Related Hospitalization

The frequencies and percentage of patients with admissions/emergency department visits for hypoglycemia, hospitalizations due to CHI or CHI-related events, visits to health care providers (family doctor, specialists, etc.) caused by CHI or CHI-related events and need for home visits by paramedics due to hypoglycemia will be summarized by week for Part 2.

Additionally, number and length (in days) of hospitalizations due to CHI, number of visits to health care providers (family doctor, specialists, etc.) caused by CHI or CHI-related events, and number of home visits by paramedics due to hypoglycemia will be summarized by week for Part 2 and for the patients in FAS.

9. Safety and Tolerability Analysis

Safety assessments will include the evaluation of AEs, clinical laboratory assessments (hematology, biochemistry, and ADAs), vital signs, physical examinations; electrocardiograms (ECGs), echocardiography, and local tolerability issues. No formal inferential analyses will be conducted for safety variables, unless otherwise specified.

All safety analyses will be summarized by treatment received within treatment period and part also by active treatment (Dasiglucagon pooling data of part 1 and part 2) and by study visit, if applicable.

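### The SAP limits the local tolerability summary to dasiglucagon, so the tables omit the blinded placebo periods that the protocol and the SAP's own general safety rule would include

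*SAP*

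**What the plan says.** On collection, SAP section 9.7 states: "Local tolerability data will be collected separately from AEs at Days 1, 2, 3, 4, 5, 6, 11, 18, and 25". Days 1 to 4 are Part 1, so both crossover periods are covered. The items collected are the nature of the reaction, whether it is at the injection site, its severity, the action taken and the likely cause (insertion site, drug, adhesive dressing or other).

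On reporting, the same section says that findings "will be summarized by part and study visit", lists nature, site, severity and action taken as the items to tabulate, and ends: "Description will be performed only on the Dasiglucagon group". Likely cause is not among the tabulated items, and no analysis set is named.

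The general rules read differently:

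- Opening text of SAP section 9, which names local tolerability among the safety assessments: "All safety analyses will be summarized by treatment received within treatment period and part also by active treatment".
- Protocol section 13.4.4 (versions 13.0 and 14.0), which also names local tolerability: "All safety analyses will be summarized by treatment received within treatment period and part and by trial visit, if applicable".
- Protocol synopsis (both versions): "local tolerability data will be summarized by treatment, where applicable".
- Protocol section 13.4.4.7, which is specific to local tolerability, asks for a summary and sets no restriction to one treatment.

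SAP section 10 lists five changes from the planned analysis. The restriction to dasiglucagon is not one of them.

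**The concern.** Matching placebo is given subcutaneously through an infusion pump, as the active drug is (protocol section 10.1). A cannula, tubing and dressing can cause reactions of their own. The German protocol (section 20.3.2) lists irritation, pain, redness, swelling and lumps at the infusion site as anticipated effects of the pump system. These overlap with the pain, redness, edema and induration that SAP 9.7 collects as local tolerability findings.

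Part 2 is dasiglucagon only (SAP section 3.4), so the Part 1 placebo period is the only within-trial comparison for such reactions. A table with dasiglucagon alone gives a reaction rate with nothing to set it against. The sponsor's own account of this risk in protocol section 6.3.6 relies on that kind of comparison: it describes site reactions in earlier trials as similarly frequent across treatment groups, placebo included. Safety and tolerability of the subcutaneous infusion is also the stated secondary objective.

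**Working it through.** SAP 9.7 gives no numerical figure to reproduce, and the sample-size calculation does not bear on this point. The check is a comparison of texts, a count of what the tables would leave out, and a gauge of how much the missing column could show.

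**1. Is a by-treatment summary applicable?** The synopsis qualifies its rule with an applicability clause. Placebo-period assessments are scheduled in SAP 9.7 and in the Schedule of Events, so data for a placebo column are planned and the clause does not remove it.

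**2. Is SAP 9.7 in line with its neighbours?** Adverse events (9.1), vital signs (9.3), ECG (9.4) and physical examination (9.6) are all summarized by treatment group. Echocardiography (9.5) is not, but it is done only at Screening and Follow-up, so no treatment comparison within Part 1 is possible. Section 9.7 is the only one that has data on both treatments and drops one of them.

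**3. What is left out.** Inputs: 12 patients, randomized 1:1 (SAP 3.2 and 3.5); two 48-hour periods, that is 2 days on each treatment; nine assessment days in total (SAP 9.7). All 12 are assumed to complete both periods.

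- Placebo patient-days: 12 × 2 = 24.
- Part 1 dasiglucagon patient-days: 12 × 2 = 24, in the same infants.
- Share of each infant's assessment days spent on placebo: 2/9 = 22%.
- Placebo patient-days tabulated under SAP 9.7: 0 of 24. Under the protocol rule: 24 of 24.

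The by-visit layout adds a further effect. With 1:1 allocation, about 12/2 = 6 infants are on dasiglucagon on Days 1 and 2 and the other 6 on Days 3 and 4. Each Part 1 visit in the table would then describe about half the infants, without showing the other half.

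**4. What the extra column could show.** Exact (Clopper-Pearson) 95% intervals for x of 12 patients with a reaction:

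- x = 0: the upper limit is 1 − 0.025^(1/12) = 0.265, so 0 to 26.5%.
- x = 3 (25%): 5.5 to 57.2%.

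For scale only, since no test is planned: if r infants react on one treatment but not the other, all in the same direction, the exact two-sided paired p-value is 2 × 0.5^r. This is 0.0625 for r = 5 and 0.031 for r = 6. Only a marked imbalance would stand out.

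**5. Do other outputs fill the gap?** The by-treatment adverse event tables do not replace this summary, because local tolerability is collected separately from adverse events (protocol 11.2.3.2, SAP 9.7). The likely-cause field could help in part, but it is not tabulated.

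**The case against.** A reader might infer that the placebo data are discarded or go unreported. The documents do not support that: SAP section 6.1.8 says all collected data will be listed, so every placebo-period record can be read patient by patient. What is lost is the summary.

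A reader might also infer that drug reactions could not be separated from cannula or adhesive reactions at all. That goes too far. The investigator records a likely cause for each reaction and, in Part 1, does so under blinding. This judgment is weaker than a placebo contrast, but it is relevant. The objection is blunted because SAP 9.7 leaves that field out of the tables.

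Three further points have weight. Local tolerability is not in the safety endpoint lists (protocol 7.2.4, SAP 2.2.1), although protocol 13.4.4 and SAP section 9 both name it as a safety assessment. Some site reactions may also be recorded as adverse events, which are tabulated with placebo; the German protocol defines adverse device effects as adverse events. This is a partial overlap.

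The strongest point is that the placebo period is not a perfectly clean control. There is no washout, the German protocol allows infusion sets to stay in place for 48 or 72 hours depending on type, and a skin reaction can outlast the infusion that caused it. A reaction that began on dasiglucagon could be counted under placebo in the second period. SAP 9.1 assigns each adverse event to the period in which it started; SAP 9.7 has no such rule. This does not justify dropping placebo, but deleting the sentence alone would be an incomplete repair.

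**Conclusion.** The concern holds as an undeclared inconsistency with a modest practical cost. SAP 9.7 omits from the summary tables data that SAP section 9, protocol 13.4.4 and the synopsis say will be summarized by treatment. The tables would therefore not show whether site reactions are as frequent on placebo given by the same route.

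The size is 24 planned placebo patient-days in at most 12 infants, assuming that all complete both periods. The comparison is descriptive and imprecise and has no bearing on the primary analysis, the key secondary analysis, alpha or power. The change is still worth making: it restores the only within-trial control for these reactions, uses data already scheduled for collection, and brings the SAP back into line with the protocol.

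**What to change.** In SAP section 9.7:

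1. Delete the sentence that restricts the description to dasiglucagon.
2. For Part 1, summarize local tolerability on the Safety Set by treatment received (dasiglucagon and placebo) within period.
3. Assign each reaction to the treatment period in which it started, as SAP 9.1 does for adverse events.
4. Add likely cause to the tabulated items.
5. For Part 2, summarize for dasiglucagon.

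If the sponsor prefers to keep the restriction, it should be declared and justified in SAP section 10, though the tables would then still lack the comparison. The cost is about one table column, one additional tabulated item and a short derivation rule. No additional assessments are needed; the attribution rule does need an onset date and time for each reaction, and the sponsor should confirm that the eCRF captures these.

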9.8. Prior/Concomitant Medication and Procedure

Concomitant medications will be coded using World Health Organization Drug Dictionary Enhanced (WHO-DDE) (Version September 01, 2018 or later) thesaurus.

Medications that started before first dose of dasiglucagon or placebo will be considered prior medications if they were stopped before first dose of dasiglucagon/placebo. Any medications ongoing at start of trial will be considered to be concomitant medication ongoing at start. If a medication starts or changed during the trial it will be considered as medication starting during the trial. Prior medication and procedure will be described by treatment sequence on the FAS.

Concomitant Medication and Procedures will be described by treatment (Part 1) and overall (Part 2) as well as for all Dasiglucagon exposure on the FAS.

Frequencies and percentages will be summarized descriptively by Anatomical Therapeutic Chemical (ATC) classification Level 4 and Preferred Name. The summary will be presented in descending order of frequency of ATC and then Preferred Name within ATC based on overall patients.

10. Changes from Planned Analysis

- To be consistent over all studies, wording of hypoglycemia episodes has been updated as “SMPG-detected hypoglycemia episodes” and “CGM-detected hypoglycemia episodes”.
- For site 101, remove IV GIR values that are assessed in between parts from statistical analysis
- Add tipping point analysis on primary endpoint
- Add sensitivity analysis on primary endpoint due to different GIR values at start of each cross-over for few patients
- Add sensitivity analysis for CGM percent time in hypoglycemia due to use of paracetamol for patients using Dexcom G4.

11. Other Planned Analysis

11.1. Pharmacokinetic Analysis

Plasma concentrations are collected on Day 5 (applicable for patients with a body weight of $\geq 4\text{kg}$, sample will only be collected if it does not compromise the total amount of blood drawn), Day 6 and Day 25. Descriptive summaries will be presented for plasma PK concentrations by study visit and infusion rate (in $\mu\text{g}/\text{kg}/\text{hr}$). Information pertaining to PK data collection will be listed.

PK analysis will be performed using PK population according to actual treatment received.

12. References

1. US Federal Register. (1998) International Conference on Harmonization; Guidance on Statistical Principles for Clinical Trials. Department of Health and Human Services: Food and Drug Administration [Docket No. 97D-0174]. Federal Register Volume 63, Number 179, pages 49583-49598. September 16, 1998.
2. ASA. (2016) Ethical Guidelines for Statistical Practice. Prepared by the Committee on Professional Ethics, April 2016. <http://www.amstat.org/about/ethicalguidelines.cfm>
4. The Royal Statistical Society: Code of Conduct, 2014.

13. Tables, Listings, and Figures

All listings, tables, and graphs will have a header showing the sponsor company name and protocol and a footer showing the version of SAS, the file name and path, and the source of the data (CRF page or listing number).

The following reporting conventions will be adopted for the presentation of study data. These conventions will enhance the review process and help to standardize the presentation with common notations.

General Reporting Conventions

- All tables and data listings will be developed in landscape orientation.
- Specialized text styles, such as bolding, italics, borders, shading, and superscripted and subscripted text will not be used in tables, figures, and data listings unless they add significant value to the table, figure, or data listing.
- Only standard keyboard characters should be used in tables and data listings. Special characters, such as nonprintable control characters, printer-specific characters, or font specific characters, will not be used on a table, figure, or data listing.
- Adverse events with missing MedDRA coding will have their system organ class and/or preferred term presented as “Not Coded” in the tables. The “Not Coded” frequencies will be sorted to the end of the tables. This will only be applicable for any deliveries sent before database lock (e.g., for dry runs).
- Programming notes may be inserted into the shells, these notes will not appear in the final output.

Population Summary Conventions

- Population sizes may be presented for each classification factor as totals in the column header as (N=xx), where appropriate.
- All population summaries for categorical variables will include all categories that were planned and for which the subjects may have had a response. Percentages corresponding to null categories (cells) will be suppressed; however, counts and percentages of missing values may be needed.
- All population summaries for continuous variables will include n, mean, SD, median, minimum, and maximum. Other summaries (e.g., number missing, geometric mean, median, quartiles, 95% CIs, and coefficient of variation [CV] or % CV) may be used as appropriate. The precision of the maximum and minimum will match the maximum precision in the data. The mean and median will have 1 additional decimal place. The SD will have 2 additional decimal places.
- All percentages are rounded and reported to a single decimal point (xx.x%).

Appendix 1: List of Abbreviations

Abbreviation	Definition
AE	adverse event
AESI	adverse events special interest
ATC	anatomical therapeutic chemical
CGM	continuous glucose monitoring
CHI	congenital hyperinsulinism
CI	confidence intervals
CRF	case report form
CSR	clinical study report
DBL	database lock
DMC	data monitoring committee
ECG	electrocardiogram
eCRF	electronic case report form
EDC	electronic data capture
EMA	European medicines agency
eTMF	electronic trial master file
EU	European Union
FAS	full analysis set
FDA	food and drug administration
GCP	good clinical practice
HR	heart rate

Abbreviation	Definition
IC or ICF	informed consent or informed consent form
ICH	international council for harmonization
ID	Identification
IDM	independent drug monitoring
IWRS	interactive web response system
MedDRA	medical dictionary for regulatory activities
N	Number
NA	not applicable
NCS	non-clinically significant
PD	protocol deviation
PE	physical examination
PG	plasma glucose
PK	pharmacokinetic
PP	per-protocol
QA	quality assurance
SAE	serious adverse event
SAP	statistical analysis plan
SAS®	a software system used for data analysis
SD	standard deviation
SDTM	study data tabulation model
SF	screen failure

Abbreviation	Definition
SMPG	self-monitored plasma glucose
SOC	system organ class
SOP	standard operating procedure
TEAE	treatment-emergent adverse event
USA	United States of America
WHO	world health organization
WHO-DD	world health organization drug dictionary
